### **8.2.2. Worst Itch – Numeric Rating Scale (WI-NRS) Pruritus Score**

Secondary efficacy endpoints relating to WI-NRS pruritus score include the following:

- Change and percent change in WI-NRS pruritus score at Weeks 1, 2, 3, 4, 5, 6, 7, 8, 9, 10, 11, 12, and 13 as compared to Baseline
- The rate of achievement of  $\geq 4$ -point reduction from Baseline in WI-NRS pruritus score at 1, 2, 3, 4, 5, 6, 7, 8, 9, 10, 11, 12, and 13 weeks after first study drug application, in subjects with Baseline WI-NRS pruritus score of at least 4

### Change in WI-NRS Pruritus Score Analysis

Change and percent change from baseline to each study week through Week 12 in average weekly WI-NRS pruritus score will be analyzed using descriptive statistics and an ANCOVA with terms for treatment group, pooled site group, baseline IGA category, and baseline WI-NRS pruritus score as covariates, by study visit. Statistical comparisons between the treatment groups will be obtained using contrasts. The LS means, standard errors, 90% and 95% CIs, and *P* values will be presented. This analysis will be based on Cohort 2 subjects in the ITT and PP populations (ANCOVA using nonimputed data only). Additionally, this analysis will be repeated for Cohort 1 subjects in the All Treated population, excluding between-treatment contrasts (due to being a single-treatment cohort).

### Rate of Achievement Analysis

In subjects with a baseline WI-NRS score  $\geq 4$ , achievement of a  $\geq 4$ -point improvement from baseline in average weekly WI-NRS score at Weeks 1, 2, 3, 4, 5, 6, 7, 8, 9, 10, 11, 12, and 13 will be analyzed using CMH tests stratified by pooled site group and baseline IGA category similar to the primary analysis in [Section 8.1](#), with the exception that missing data will not be replaced. Odds ratios and 90% and 95% CIs of the odds ratios will be provided. Additionally, the 90% and 95% Wilson CIs for proportion of successes in each treatment group will be presented. This analysis will be based on Cohort 2 subjects in the PRU4 population (nonimputed data only).

Additionally, this analysis will be repeated for Cohort 1 subjects in the All Treated population, excluding the CMH test (due to being a single-treatment cohort).

### 8.2.3. Hand Eczema Severity Index (HECSI)

The secondary efficacy endpoints relating to HECSI are:

- Change and percent change in HECSI score at Weeks 2, 4, 8, 12, and 13 compared to Baseline
- Achievement of HECSI-75

The HECSI is an instrument used in clinical trials to rate the severity of 6 clinical signs of hand eczema and the extent of the lesions on each of 5 hand areas by use of standard scales. The total HECSI score is based on a 4-point severity scale ranging from 0 (none/absent) to 3 (severe) and a 5-point scale rating the affected area(s) ranging from 0 (0% affected area) to 4 (76% to 100% affected area). Derivations for each of the subscores and the total score can be found in [Section 6.1.7](#).

Change and percent change from baseline to Weeks 2, 4, 8, 12, and 13 in HECSI subscores (Fingertips, Fingers [except Tips], Palm of Hands, Back of Hands, and Wrists) and total score will be analyzed using descriptive statistics and an ANCOVA with terms for treatment group, pooled site group, baseline IGA category, and baseline HECSI score as covariates, by study visit. Statistical comparisons between the treatment groups will be obtained using contrasts. The LS means, standard errors, 90% and 95% CIs, and *P* values will be presented. This analysis will be based on Cohort 2 subjects in the ITT population (nonimputed data only) and PP population (ANCOVA using nonimputed data only). Additionally, this analysis will be repeated for Cohort 1 subjects in the All Treated population, excluding between-treatment contrasts (due to being a single-treatment cohort).

Frequencies and percentages of subjects achieving HECSI-75 will be presented by study visit and treatment group. This endpoint will be analyzed using CMH tests stratified by pooled site group and baseline IGA category similar to the primary analysis in [Section 8.1](#), with the exception that missing data will not be replaced. Odds ratios and 90% and 95% CIs of the odds ratios will be provided. Additionally, the 90% and 95% Wilson CIs for proportion of subjects achieving 75% reduction in each treatment group will be presented. This analysis will be based on Cohort 2 subjects in the ITT and PP populations (nonimputed data only).

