## 4. STATISTICAL ANALYSIS AND REPORTING

### 4.1. Introduction

Data processing, tabulation of descriptive statistics, calculation of inferential statistics, and graphical representations will primarily use SAS (release 9.4 or higher). If the use of other software is warranted, the final statistical methodology report will detail what software was used for what purposes.

Continuous (quantitative) variable summaries will include the number of subjects (n) with non-missing values, mean, standard deviation (SD), median, minimum, and maximum.

Categorical (qualitative) variable summaries will include the frequency and percentage of subjects who are in the particular category or each possible value. In general, the denominator for the percentage calculation will be based upon the total number of subjects in the study population for each treatment group, unless otherwise specified.

The minimum and maximum will be reported with the same degree of precision (i.e., the same number of decimal places) as the observed data. Measures of location (mean and median) will be reported to 1 degree of precision more than the observed data and measures of spread (SD, standard error [SE]) will be reported to 2 degrees of precision more than the observed data.

Percentages will be presented to 1 decimal place, unless otherwise specified.

Unless otherwise indicated, all statistical tests will be conducted at the 0.1 significance level using 2-tailed tests, and *P* values will be reported. For the purposes of statistical comparisons, the vehicle BID and vehicle QD groups will be pooled together. Testing will be performed for:

- ARQ-252 cream 0.3% QD versus vehicle cream (all dose frequencies)
- ARQ-252 cream 0.3% BID versus vehicle cream (all dose frequencies)
- ARQ-252 cream 0.1% QD versus vehicle cream (all dose frequencies)
- ARQ-252 cream (all strengths and dose frequencies) versus vehicle cream (all dose frequencies)
- ARQ-252 cream 0.3% (all dose frequencies) versus vehicle cream (all dose frequencies)

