Corresponding 90% and 95% confidence intervals (CIs) will be presented for statistical tests. Testing will be performed for the primary endpoint of IGA clear or almost clear, for change from baseline in the HECSI score, and for the percent change from baseline in the HECSI score; however, *P* values will be provided for informational purposes for other endpoints as specified in [Section 8](#). The primary statistical comparisons and evaluations of secondary endpoints will not be adjusted for multiplicity.

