datasets, depending on the number of imputed monotone datasets that are required. The seed or number of imputed datasets may be changed after unblinding in case of any issues with the imputation process, and it will be documented in the CSR if any change is required.

3. For each completed dataset, compute the necessary derived variables. The dichotomous success rate (clear or almost clear) will be derived. The results obtained will be analyzed using the CMH analysis for each of the complete analysis data sets stratified by baseline IGA score and site. The results will be combined into one multiple imputation inference (odds ratio, associated CI, and *P* value) using PROC MIANALYZE as illustrated below (Ratitch 2013).

This approach to imputation should be superior to other strategies such as carrying forward the last available observation, which may yield unrealistic imputed values. Also, the use of multiple imputation avoids the problem of artificially increasing power through data imputation associated with single-imputation methods because it accounts for the uncertainty associated with the imputation. Other missing data will not be imputed, with the exception of incomplete dates as described in Section 6.1.8. For responder analyses, missing data will be treated as a nonresponse with the exception of IGA. Only observed data will be summarized using descriptive statistics.

The SAS pseudo code for the multiple imputation process is listed below:

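### HECSI change and percent change, two of the three outcomes named for testing, rest only on visit-wise observed-case ANCOVA, with no missing-data sensitivity analysis

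*SAP*

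**What the plan says.** SAP 4.1 sets the level: "all statistical tests will be conducted at the 0.1 significance level using 2-tailed tests". It then limits where testing applies: "Testing will be performed for the primary endpoint of IGA clear or almost clear, for change from baseline in the HECSI score". HECSI percent change is the third outcome on that list, and P values outside the list are described as informational. HECSI therefore supplies two of the three tested outcomes.

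The HECSI model in SAP 8.2.3 is "an ANCOVA with terms for treatment group, pooled site group, baseline IGA category, and baseline HECSI score as covariates, by study visit". No post-baseline HECSI value enters it. The data sets named there are the "ITT population (nonimputed data only) and PP population (ANCOVA using nonimputed data only", so neither population has an imputed version. SAP 6.1.4 sets the general rule outside IGA: "Other missing data will not be imputed". Partial dates are the exception.

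IGA is treated differently. SAP 6.1.4 imputes it from the IGA scores at previous visits, treatment and pooled site. SAP 8.2.1 runs the IGA change ANCOVA on both imputed and nonimputed data, although its P values are only informational. The sensitivity analyses in SAP 8.1.2 cover the primary endpoint alone.

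**The concern.** IGA and HECSI share one row of the Cohort 2 visit schedule, so the same kind of earlier-visit information exists for both. The plan uses it for IGA and leaves it out of the Week 12 HECSI contrast. An observed-case ANCOVA is unbiased if dropout is random, or depends only on treatment and the baseline covariates in the model. It has no protection if subjects leave because of how they responded after baseline.

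That mechanism is plausible here. SAP 2.2.1.1 mentions treatment discontinuation for lack of effect, and SAP 3.2 assumes 45% response on active against 15% on vehicle. If non-response leads to leaving the study, missingness could depend on response and differ by arm. SAP 6.2 adds that HECSI cannot be collected remotely during COVID-19 disruption. At stake is the size of a tested treatment difference, with nothing planned that would show how far it depends on the missing-data assumption.

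**Working it through.** **Figure to reproduce.** The documents give no HECSI effect size, SD, correlation or power. The nearest stated figure is power for IGA, about 85% for 55 against 28; the pooled-variance chi-square formula gives 89.3%. That concerns another outcome and does not enter below.

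**Inputs from the documents.** 61 subjects in an ARQ-252 0.3% arm; pooled vehicle 31 + 31 = 62; overall dropout 10%, not split by arm or reason (Protocol 6.1.1).

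**Assumed.** True Week 12 difference 0.5 SD in favour of active, between-visit correlation 0.5 or 0.7, dropout after Week 8.

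**Where the bias comes from.** Let d be the dropout fraction in an arm and m the amount by which dropouts' mean Week 12 outcome is worse than the whole arm's, in SD. Completers then look better than the arm by m × d/(1 − d). With A for active and V for vehicle:

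bias toward zero = m_V × d_V/(1 − d_V) − m_A × d_A/(1 − d_A).

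If d and m match across arms, the bias is zero. If more poor responders leave active, the sign reverses.

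**Simulation.** 2,000 runs per scenario compared the Week 12 observed-case ANCOVA with an estimate that also conditions on Weeks 2, 4 and 8. Positive bias is toward zero; each pair is for correlation 0.5 / 0.7.

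| Dropout mechanism | Active/vehicle dropout | Observed-case bias, SD | % of 0.5 SD | Bias using earlier visits, SD |
|---|---|---|---|---|
| Random | 10%/10% | 0.002 / 0.000 | 0 / 0 | 0.002 / 0.000 |
| Random | 5%/20% | −0.008 / 0.000 | −2 / 0 | −0.006 / 0.000 |
| Baseline severity | 10%/10% | 0.004 / −0.002 | 1 / 0 | 0.004 / −0.001 |
| Poor response, both arms | 10%/10% | 0.005 / 0.003 | 1 / 1 | 0.005 / 0.003 |
| Poor response, both arms | 8%/12% | 0.005 / 0.009 | 1 / 2 | −0.006 / −0.003 |
| Poor response, both arms | 5%/20% | 0.042 / 0.039 | 8 / 8 | −0.001 / 0.000 |
| Poor response, both arms | 10%/30% | 0.054 / 0.047 | 11 / 9 | 0.000 / −0.003 |
| Poor response, vehicle only | 10%/10% | 0.025 / 0.025 | 5 / 5 | −0.005 / −0.003 |
| Poor response, vehicle only | 10%/20% | 0.051 / 0.055 | 10 / 11 | −0.007 / 0.002 |
| Opposite in the two arms | 10%/10% | 0.059 / 0.051 | 12 / 10 | −0.002 / −0.004 |

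Simulation error is about 0.170/√2000 = 0.004 SD, so entries up to about 0.008 are compatible with zero.

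**Cross-check with the formula.** At 5%/20% the multiplier is 0.20/0.80 − 0.05/0.95 = 0.250 − 0.053 = 0.197, so a bias of 0.042 implies m = 0.042/0.197 = 0.21 SD. The same m at 8%/12% gives (0.136 − 0.087) × 0.21 = 0.010 SD, or 2%. For vehicle-only at 10%/10% it gives 0.111 × 0.21 = 0.023 SD, or 5%. Both agree with the table.

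**Against the standard error.** In the biased scenarios the shift runs from 0.025/0.167 = 0.15 to 0.051/0.133 = 0.38 of the observed-case standard error.

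**Precision.** The estimate using earlier visits had an empirical standard error about 1% to 3% smaller, for example 0.163 against 0.165, and 0.143 against 0.148.

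**Sensitivity to the dropout model.** On the percent-change scale (true difference −22 points, SD 35 to 42, adjacent-visit correlation 0.7, dropout driven by the prior visit), 7%/11% to 17%/24% dropout gave −20.5 to −19.6, a shrinkage of 1.5/22 = 7% to 2.4/22 = 11%. Another such model, without baseline covariates, gave −21.7 to −21.1 at about 8–9%/10–12% (0.3/22 = 1% to 0.9/22 = 4%). The size depends on how closely dropout follows response.

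**The case against.** The strongest reply is that the SAP follows the protocol. Protocol 6.2.3 specifies ANCOVA for continuous secondary endpoints, and Protocol 6.1 provides multiple imputation for IGA only. HECSI is a secondary endpoint in a phase 2b study with no multiplicity control, and every biased scenario run shrank the effect, so the risk shown is lost power rather than a false positive. The shift is also well under half a standard error. A sensitivity analysis might seem enough, without changing the main model.

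Some stronger readings also fail:

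- A reader might infer that the Week 12 difference is biased. The documents give no dropout by arm or reason, so neither the presence nor the size of bias can be established.
- A reader might infer that dropouts' data are thrown away. Earlier values still enter their own visits' ANCOVAs. An early-termination HECSI counts at Week 12 if no scheduled value exists and it falls on Days 71 to 90 (SAP 6.1.5). Protocol 4.8 and 4.9 separate stopping product from leaving the study, so a subject off product can still supply Week 12 data.
- A reader might infer a breach of the treatment-policy estimand. SAP 2.2.1.1 writes that estimand for the primary IGA endpoint, and the strategy addresses intercurrent events, not the missing-data model.

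These points limit the claim but do not remove it. Tested outcomes still rest on a stronger missingness assumption than the primary analysis makes for IGA, without a check, while the informational IGA change analysis has one.

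**Conclusion.** The point holds in conditional form. For the two HECSI outcomes named for testing, the Week 12 contrast ignores Weeks 2, 4 and 8 HECSI from subjects missing at Week 12, and no analysis probes the effect of that. The bias is about 5% to 12% of an assumed 0.5 SD effect, toward zero, when dropout follows post-baseline response and differs between arms in rate or mechanism. It is about 0% to 2% when dropout is random, driven by baseline, or similar in both arms. These sizes rest on assumed effect, correlation and dropout models, and the direction depends on which arm loses its poorer responders. The documents do not settle which case applies. This is a change that should be made, not a demonstrated error in the result.

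**What to change.** Before unblinding, amend SAP 8.2.3 for HECSI total score change and percent change. Use a mixed model for repeated measures over Weeks 2, 4, 8 and 12, with treatment, visit, treatment × visit, baseline HECSI, baseline HECSI × visit, baseline IGA category and pooled site, unstructured covariance, and the contrasts already listed in SAP 8.2. Alternatively, impute HECSI from its earlier visits as SAP 6.1.4 does for IGA, and run the planned ANCOVA on the completed data. Keep the observed-case ANCOVA as supportive; comparing the two then shows how much the missing-data assumption matters. Record the change in SAP Section 10.

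The cost is a paragraph of SAP text, modest programming and a documented departure from the protocol's ANCOVA. No new data are needed and precision is essentially unchanged. Either method still assumes that missingness is explained by the data observed; neither covers dropout that depends on the unseen Week 12 value itself.

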### 8.2.4. Pain Numeric Rating Scale (NRS) Score

Secondary efficacy endpoints relating to Pain NRS score include the following:

- Change and percent change in Pain NRS score from Baseline to Weeks 1, 2, 3, 4, 5, 6, 7, 8, 9, 10, 11, 12, and 13
- The rate of achievement of  $\geq 4$ -point reduction from Baseline in Pain NRS score at 1, 2, 3, 4, 5, 6, 7, 8, 9, 10, 11, 12, and 13 weeks after first application of study drug with Baseline Pain NRS score of at least 4

- The rate of achievement of  $\geq 3$ -point reduction from Baseline in Pain NRS score at 1, 2, 3, 4, 5, 6, 7, 8, 9, 10, 11, 12, and 13 weeks after first application of study drug in subjects with baseline Pain NRS score of at least 3
- The rate of achievement of  $\geq 2$ -point reduction from Baseline in Pain NRS score at 1, 2, 3, 4, 5, 6, 7, 8, 9, 10, 11, 12, and 13 weeks after first application of study drug in subjects with baseline Pain NRS score of at least 2

The Pain NRS score is the subject's assessment of worst pain intensity over the past 24 hours on a scale of 0 to 10, where 0 = "no pain" and 10 = "worst possible pain".

#### Change in Pain NRS Score Analysis

Change and percent from baseline to 1, 2, 3, 4, 5, 6, 7, 8, 9, 10, 11, 12, and 13 weeks after first application of study drug in average weekly Pain NRS score will be analyzed using descriptive statistics and an ANCOVA with terms for treatment group, pooled site group, baseline IGA category, and baseline Pain NRS score as covariates, by study visit. Statistical comparisons between the treatment groups will be obtained using contrasts. The LS means, standard errors, 90% and 95% CIs, and *P* values will be presented. This analysis will be based on Cohort 2 subjects in the ITT population (nonimputed data only). Additionally, this analysis will be repeated for Cohort 1 subjects in the All Treated population, excluding between-treatment contrasts (due to being a single-treatment cohort).

#### Rate of Achievement Analysis

In subjects with a baseline Pain NRS score  $\geq 4$ , achievement of a  $\geq 4$ -point improvement from baseline in average weekly Pain NRS score at 1, 2, 3, 4, 5, 6, 7, 8, 9, 10, 11, 12, and 13 weeks after first application of study drug will be analyzed using CMH tests stratified by pooled site group and baseline IGA category similar to the primary analysis in [Section 8.1](#), with the exception that missing data will not be replaced. Odds ratios and 90% and 95% CIs of the odds ratios will be provided. Additionally, the 90% and 95% Wilson CIs for proportion of successes in each treatment group will be presented. This analysis will be based on Cohort 2 subjects in the PNR4 population (nonimputed data only). Additionally, this analysis will be repeated for Cohort 1 subjects in the PNR4 population, excluding the CMH test (due to being a single-treatment cohort).

This analysis will furthermore be repeated on subjects with a baseline Pain NRS score  $\geq 3$  and a baseline Pain NRS score  $\geq 2$  for achievement of a  $\geq 3$ -point improvement from baseline and a  $\geq 2$ -point improvement from baseline, respectively. This analysis will be performed on subjects in the PNR3 and PNR2 populations, with each cohort presented separately (where the CMH testing in Cohort 1 will be excluded).

### 8.2.5. Quality of Life in Hand Eczema Questionnaire (QOLHEQ)

The secondary efficacy endpoint relating to QOLHEQ is:

- Change and percent change from baseline in overall QOLHEQ score at each study visit

The construct HRQOL includes all impairments or limiting conditions caused by the health state of an individual. The QOLHEQ is a disease specific instrument, thereby only assessing impairments caused by hand eczema. It consists of 30 items which can be summarized according to four domains of HRQOL: Impairments because of (1) symptoms, (2) emotions, (3) limitations in functioning, or (4) because of treatment and prevention. Derivations for each of the subscores and the total score can be found in [Section 6.1.7](#).

Change and percent change from baseline to Weeks 2, 4, 8, 12, and 13 in QOLHEQ subscores (Symptoms, Emotions, Limitations in Function, Treatment and Prevention) and total score will be analyzed using descriptive statistics and an ANCOVA with terms for treatment group, pooled site group, baseline IGA category, and baseline overall QOLHEQ score as covariates, by study visit. Statistical comparisons between the treatment groups will be obtained using contrasts. The LS means, standard errors, 90% and 95% CIs, and *P* values will be presented. These analyses will be based on Cohort 2 subjects in the ITT population (nonimputed data only).

### 8.2.6. Percent Body Surface Area (BSA) Affected by Disease

The secondary efficacy endpoint relating to percent BSA affected by disease (dorsal [left hand], dorsal [right hand], palmar [left hand], palmar [right hand], total hand) is:

- Percent BSA affected by disease and % change from baseline in BSA affected by disease at baseline, 2 weeks, 4 weeks, 8 weeks, 12 weeks, and 13 weeks

Change and percent change from baseline to Weeks 2, 4, 8, 12, and 13 in percent BSA affected by disease will be analyzed using descriptive statistics and an ANCOVA with terms for treatment group, pooled site group, baseline IGA category, and baseline percent BSA affected by disease as covariates, by study visit. Statistical comparisons between the treatment groups will be obtained using contrasts. The LS means, standard errors, 90% and 95% CIs, and *P* values will be presented. This analysis will be based on Cohort 2 subjects in the ITT population (nonimputed data only). Additionally, this analysis will be repeated for Cohort 1 subjects in the All Treated population, excluding between-treatment contrasts (due to being a single-treatment cohort).

### 8.3. Exploratory Efficacy Analysis

The exploratory efficacy endpoint is:

- Change from Baseline in Nail Dystrophy at each visit

In subjects with a nail dystrophy at baseline, change in number of millimeters of normal-appearing nail distal to the cuticle will be summarized by treatment group and study visit. Since the number of millimeters of normal-appearing nail distal to the cuticle at baseline was not collected, it is assumed to be 0 mm; similarly, for subjects with nail dystrophy at baseline, if they report having no normal-appearing nail distal to the cuticle after baseline, their result is imputed as 0 mm (as this amount is not collected in the eCRF). This analysis will be based on Cohort 2 subjects in the ND population (nonimputed data only).

